3.0 OBJECTIVE(S), HYPOTHESIS(ES), AND ENDPOINT(S)

3.1 Primary Objective(s), Hypothesis(es), and Endpoint(s)

(1) **Objective:** To determine the ORR through the Immune Response Evaluation Criteria in Solid Tumors (iRECIST) [Seymour et al., 2017].

Hypothesis: The combination of PD-1 and PARP inhibition will result in an immune overall response for patients with recurrent cervical carcinoma.

Primary Endpoint: Immune overall response rate (iORR)

3.2 Secondary Objective(s), Hypothesis(es), and Endpoint(s)

(1) **Objective:** To determine PFS and OS, defined as time from treatment initiation to disease progression or death.

Hypothesis: The combination of PD-1 and PARP inhibition will result in a progression-free survival advantage for patients with recurrent cervical carcinoma.

Secondary Endpoint: Progression-free survival (PFS)

(2) **Objective:** To evaluate safety and tolerability per the Common Terminology Criteria for Adverse Events (CTCAEv5.0) [Common Terminology Criteria for Adverse Events https://ctep.cancer.gov/protocoldevelopment/electronic_applications/docs/CTCAE_v5_Quick_Reference_8.5x11.pdf. Accessed September 30, 2018].

Hypothesis: Combination of PD-1 and PARP inhibitors is tolerable in patients with recurrent cervical cancer.

Secondary Endpoint: Toxicities associated with the regimen

(3) **Objective:** To evaluate if baseline tumor deficiencies in the Fanconi Anemia pathway are associated with antitumor responses to the combination as assessed by the FATS1 assay, performed on archived paraffin embedded tumor tissues.

Hypothesis: Deficiencies in homologous recombination (HR) repair based on the Fanconi Anemia Triple Stain Immunofluorescence (FATS1) assay will predict a higher iORR to the combination of pembrolizumab and olaparib in patients with cervical cancer.

Secondary Endpoint: Immune overall response rate (iORR)

(4) **Objective:** To determine duration of response (DoR).

Hypothesis: The combination of PD-1 and PARP inhibition will result in a duration of response (DoR), defined as time from documentation of tumor response to disease progression, in this cohort.

Secondary Endpoint: Duration of response (DoR)

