six patients. If intolerable toxicities arise after three or more cycles in patients otherwise experiencing clinical benefit, patients will have the option of continue pembrolizumab as monotherapy. Special attention will be placed on persistent grade 3 or higher anemia, as myelodysplastic syndromes have been described in around 1.5% of patients receiving olaparib in previous trials[Pujade-Lauraine et al., 2017; Robson et al., 2017; Ledermann et al., 2012; Moore et al., 2014]. Hematologic consultation (with bone marrow aspiration as needed) will be requested for patients developing persistent anemia.

Patients will be followed for three (3) years or until time of death. ORR, PFS, and OS will be determined. Correlative studies will determine the functional status of the Fanconi Anemia pathway promoting homologous recombination repair as well as the microbiome composition in responsive and non-responsive patients. In addition, tumor mutation burden, MSI, and PD-L1 expression will be correlated with Fanconi Anemia pathway status and response to therapy.

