5.8 Participant Replacement Strategy

We anticipate enrollment of 48 patients for which tumor and toxicity assessments following pembrolizumab/olaparib administration can be made. We will replace patients enrolled for which clinical trial discontinuation was performed prior to any administration of pembrolizumab or those for which pembrolizumab is discontinued due to acute hypersensitivity reactions during the first administration of pembrolizumab. An attempt will be made to assess tumor response in all enrolled patients as specified in the protocol. Patients experiencing clinical deterioration after two doses of pembrolizumab, will be considered treatment failures, will count as tumor progression, and will not be replaced.

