6.1.2.6.2 Tumor Imaging During the Study

The first on-study imaging assessment should be performed at 9 weeks (± 7 days) from the date of first dose. Subsequent tumor imaging should be performed every 9 weeks (± 7 days) or more frequently if clinically indicated. After 52 weeks (± 7 days), participants who remain on treatment will have imaging performed every 12 weeks (± 7 days). Imaging timing should follow calendar days and should not be

adjusted for delays in cycle starts. Imaging should continue to be performed until disease progression is identified by the Investigator.

Objective response should be confirmed by a repeat imaging assessment. Tumor imaging to confirm PR or CR should be performed at least 4 weeks after the first indication of a response is observed. Participants will then return to regular scheduled imaging every 9 weeks, starting with the next scheduled imaging time point. Participants who receive additional imaging for confirmation do not need to undergo the next scheduled tumor imaging if it is less than 4 weeks later; tumor imaging may resume at the subsequent scheduled imaging time point.

Per iRECIST (Section 7.1.2.6.6), disease progression should be confirmed by the site 4 to 8 weeks after first radiologic evidence of PD in clinically stable participants. Participants who have unconfirmed disease progression may continue on treatment at the discretion of the investigator until progression is confirmed by the site provided they have met the conditions detailed in Section 7.1.2.6.6. Participants who receive confirmatory imaging do not need to undergo the next scheduled tumor imaging if it is less than 4 weeks later; tumor imaging may resume at the 1.2.6.6.subsequent scheduled imaging time point, if clinically stable. Participants who have confirmed disease progression by iRECIST, as assessed by the site, will discontinue study treatment. Exceptions are detailed in Section 7.

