6.1.2.6.3 End of Treatment and Follow-up Tumor Imaging

In participants who discontinue study treatment, tumor imaging should be performed at the time of treatment discontinuation (± 4 week window). If previous imaging was obtained within 4 weeks prior to the date of discontinuation, then imaging at treatment discontinuation is not mandatory. In participants who discontinue study treatment due to documented disease progression and the investigator elects not to implement iRECIST, this is the final required tumor imaging.

For participants who discontinue study treatment without documented disease progression, every effort should be made to continue monitoring their disease status by tumor imaging using the same imaging schedule used while on treatment (every 9 weeks in Year 1 or every 12 weeks after Year 1) to monitor disease status until the start of a new anticancer treatment, disease progression, pregnancy, death, withdrawal of consent, or the end of the study, whichever occurs first.

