7.0 STATISTICAL ANALYSIS PLAN

7.1 Statistical Analysis Plan Summary

7.2 Statistical Analysis Plan

Sample size calculation: Single-Stage design will be used for this study [A'Hern, 2001; Fleming, 1982]. The study will require 48 subjects to decide whether the proportion responding (P), is less than or equal to 0.130 or greater than or equal to 0.280. If the number of responses is 10 or more, the hypothesis that $P \leq 0.130$ is rejected with a target error rate of 0.100 and an actual error rate of 0.087. If the number of responses is nine or less, the hypothesis that $P \geq 0.280$ is rejected with a target error rate of 0.100 and an actual error rate of 0.099.

Efficacy analyses: The iORR will be defined as the proportion of patients with an “immune” complete response (iCR) or “immune” partial response (iPR). For the primary iORR analysis in all the treated population, patients with an iCR or iPR will be counted as successes and all other patients (including those with missing response information) will be counted as failures. The percentage of iORR with its 95% confidence interval (CI) will be presented.

Progression free survival (PFS) will be defined among all treated patients as the time from first dose of study drug until the first date of either disease progression or death due to any cause. The date of disease progression will be defined as the earliest date of disease progression based on central review. For patients whose disease has not progressed at the time of the analysis, censoring will be performed using the date of the last valid disease assessment. The data will be analyzed by the Kaplan-Meier method. The median PFS time and 95% CI will be recorded.

Overall survival (OS): Median OS will be defined as the time from the beginning of study drug treatment until death due to any cause. For patients who have not died at the time of the analysis, censoring will be performed using the date the patient was last known to be alive. The data will be analyzed by the Kaplan-Meier method. The median OS and 95% CI will be recorded.

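### Duration of response is defined to progression only and has no analysis in Section 7.2; if responders die without documented progression and are censored, durability would be overstated

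*Combined protocol and SAP*

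**What the plan says.** Section 3.2, objective 4, contains the only definition of DoR: "defined as time from documentation of tumor response to disease progression".

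The neighbouring endpoints are defined differently. Objective 1 of the same section introduces PFS and OS together, "defined as time from treatment initiation to disease progression or death". Section 7.2 runs PFS from first dose "until the first date of either disease progression or death due to any cause", and for patients without progression "censoring will be performed using the date of the last valid disease assessment". That censoring rule is given for PFS only.

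Section 7.2 covers iORR, PFS, OS, safety, FATSI status, immune-related PFS and the microbiome. It has no paragraph on DoR, and so no event definition, censoring rule, estimator or treatment of death.

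Three other places bear on the point:

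- Section 6.1.2.6.3: off-treatment disease monitoring ends at a new anticancer treatment, "disease progression, pregnancy, death, withdrawal of consent, or the end of the study, whichever occurs first".
- Section 5.8: "Patients experiencing clinical deterioration after two doses of pembrolizumab, will be considered treatment failures, will count as tumor progression". The rule sits in the replacement strategy and mentions neither death nor DoR.
- Section 2.0: "Patients will be followed for three (3) years or until time of death".

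**The concern.** Death ends a response as surely as progression does. Under a progression-only definition, a responder who dies with no progression on record contributes no event. The usual handling is then to censor her, which treats her as still at risk of a later progression. In an advanced-cancer population that censoring is unlikely to be uninformative, and it pushes the estimate towards longer responses.

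Such deaths are possible here. Scans are 9 weeks apart in the first year and 12 weeks apart after week 52 (Section 6.1.2.6.2), so a patient can die between scans. The population has stage IV, unresectable or recurrent disease after failed first-line therapy, and is followed for up to three years.

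What is at stake is the reading of a named secondary endpoint. Because Section 7.2 is silent, the treatment of deaths would also be settled after they had been seen, in an open-label single-arm trial.

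**Working it through.** **1. How many responders DoR will rest on.** The plan states no figure for DoR, so I start from the only design figures, in Section 7.2: N = 48, success at 10 or more responses, null rate 0.130, target rate 0.280, actual errors 0.087 and 0.099. Exact binomial calculation reproduces them:

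- P(X ≥ 10 | 48, 0.13) = 0.0865
- P(X ≤ 9 | 48, 0.28) = 0.0995, so power is 0.9005

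Expected responders are 48 × 0.28 = 13.4 at the target rate and 48 × 0.13 = 6.2 at the null. A trial that just succeeds has 10. One death among 13 responders is 1/13 = 7.7%; two among 10 is 2/10 = 20%.

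**2. Direction.** Changing a death from an event to a censored time leaves every risk set as it was and removes one downward step from the Kaplan-Meier curve. The curve can stay the same or rise. It cannot fall.

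**3. Size, under stated assumptions.** Let the true median time to progression or death be m, with exponential times and total hazard λ = ln 2 / m. Let f be the share of DoR endings that are deaths without documented progression. Progression then has hazard (1 − f)λ. With deaths censored, the Kaplan-Meier curve tends to exp(−(1 − f)λt), whose median is

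ln 2 / ((1 − f)λ) = m / (1 − f).

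Assumed, because the documents give neither: m = 12 months and f from 5% to 30%. The simulation uses 13 responders, 32 months of follow-up after response (three years less an assumed four months to response) and 5,000 runs per value of f. The simulated columns are the median of the Kaplan-Meier medians.

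| f | 1/(1 − f) | Limiting median, deaths censored (months) | Simulated, death as event | Simulated, death censored | Chance of at least one such death |
|---|---|---|---|---|---|
| 5% | 1.05 | 12.6 | 11.9 | 12.8 | 44% |
| 10% | 1.11 | 13.3 | 12.0 | 13.5 | 68% |
| 20% | 1.25 | 15.0 | 12.0 | 15.2 | 91% |
| 30% | 1.43 | 17.1 | 12.1 | 17.4 | 98% |

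In no run did the death-censored median fall below the death-as-event median, as step 2 requires.

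**4. If the median is not reached.** The same model lifts the curve itself from S to S^(1 − f). Where the true proportion still in response is 50%, the estimate tends to 0.5^0.9 = 54%, 0.5^0.8 = 57% or 0.5^0.7 = 62% for f = 10%, 20% or 30%.

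**The case against.** The strongest reply is that the documents never say deaths are censored for DoR. They give no DoR censoring rule at all. A reader might infer that DoR is overestimated in this trial, but the text does not support that. Bias needs two things: a responder must die without recorded progression, and the analyst must censor her. This objection stands, and the conclusion is conditional for that reason.

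Second, Section 5.8 may already turn some of these deaths into progressions. The first on-study scan is at 9 weeks, by which time three doses are scheduled (weeks 0, 3 and 6). A scan-documented responder who later declines clinically would therefore normally be past the two-dose mark. This stands in part. The rule is written for replacement, is not tied to DoR, and would not reach a sudden death or one from toxicity or an unrelated cause. It lowers the plausible f but does not complete the endpoint.

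Third, the size has no support in the documents. No rate of death without progression is given, the 12-month median is assumed, and f is a share of DoR endings. That equals a share of responders only if no responder is censored for another reason. In the pembrolizumab study described in Section 4.1.1 the median response duration was not reached; if that recurs, there is no median to inflate, although the curve would still be lifted. All this stands, so the figures are illustrations.

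Fourth, a reader might infer that the harm lies in a biased comparison with that pembrolizumab study. The documents plan no such comparison and do not say how that study treated deaths. The time-to-event measure that Section 7.2 singles out for comparison is 20-week immune-related PFS.

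Finally, DoR carries no test, and deaths stay visible in PFS and OS. That limits the consequence without supplying the missing definition.

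**Conclusion.** The point holds in conditional form. DoR is defined once, without death, and has no analysis in Section 7.2, while PFS counts death in both places where it is defined. Followed literally, a responder's death without documented progression is not an event. If it is censored, the error can only be towards longer responses.

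The inflation of 11%, 25% or 43% in the median rests on exponential times and an assumed f of 10%, 20% or 30%. The true f is unknown and may be smaller if the Section 5.8 rule is applied to DoR. With 10 to 13 responders, one or two such deaths would be about 8% to 20% of the DoR set, enough to move a descriptive estimate.

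The reach is limited: the primary iORR analysis, N = 48, the cut-off of 10 and both error rates do not depend on DoR.

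**What to change.** In Sections 3.2 and 7.2:

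- Define DoR among patients with iCR or iPR as the time from first documented response to the earlier of disease progression or death from any cause.
- Censor responders without an event at the last valid disease assessment, as for PFS.
- Report the Kaplan-Meier median with its 95% CI.
- State which progression date serves both DoR and PFS. This needs its own sentence, because copying the PFS wording would carry its open questions into DoR. Section 7.2 dates progression by central review, whereas Section 6.1.2.6.6 gives iRECIST assessment to the investigator and Section 6.1.2.6.5 makes RECIST 1.1 the primary measure for the progression date. Under Appendix 4, the date could be the first unconfirmed progression (iUPD) or the confirmed one (iCPD).
- Say whether the clinical-deterioration rule in Section 5.8 counts as progression for DoR.

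The cost is a few sentences of protocol and SAP text. Death dates are already collected for OS, so no new data are needed. The one downside is that reported DoR may be slightly shorter.

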3.3 Exploratory Objective(s)

(1) **Objective:** To determine whether increased baseline TMB, other deficiencies in DNA damage repair mechanisms and PD-L1 expression correlate with FATSI negativity, and if these findings are independently associated with response to therapy.

[figure not shown]
4.0 BACKGROUND & RATIONALE

Excitement has been generated following the identification of mutations on the BRCA genes as potential predictors of response to PARP inhibitors and recent clinical trials demonstrating antitumor activity with PARP inhibitors in cancer patients with germline BRCA deficiency [Bryant et al., 2005; Farmer et al., 2005; Tutt et al., 2009; Fong et al., 2009; W Audeh et al., 2010]. The rationale behind these observations is that the BRCA genes are involved in homologous recombination (HR), an example of double-strand break repair, and patients with inherited BRCA germline heterozygosity who developed cancer had acquired BRCA homozygous deficiency in their tumors. The resulting genetic instability becomes an advantage for the tumor to perpetuate. Targeting an additional repair pathway, such as base excision repair through PARP inhibition would induce inability for the tumor to survive, an example of a concept commonly called synthetic lethality. The main role of PARP is to detect and initiate an immediate cellular response to metabolic, chemical, or radiation-induced single-strand breaks by signaling the enzymatic machinery in single-strand breaks.

The BRCA genes collaborate with several others in the Fanconi Anemia (FA) HR pathway [Bagby, 2003; D'Andrea et al., 2003; Reid et al., 2007; Xia et al., 2007; Smogorzewska et al., 2007; Kim et al., 2011; Vaz et al., 2010; Machida et al., 2006; Meetei et al., 2004; Garcia-Higuera et al., 2000]. Seventeen complementation groups/genes plus other interactive proteins have been described. Monoubiquitination of FancD2 and FancI by an FA core complex followed by nuclear co-localization with other DNA damage

response proteins result in the formation of nuclear repair foci, thus foci formation is the focal functional output of this pathway (Fig 1). Based on this, we developed the FATSI Assay, an immunofluorescence based method that detects FancD2/DAPI/Ki67 and permits the observation of FancD2 foci formation (or lack thereof) in the nucleus of proliferating cells in paraffin embedded tumor tissues [Duan et al., 2013]. We also developed a targeted FA sequencing panel to evaluate potential genetic defects resulting in Fanconi Anemia functional deficiency and confirmed the ability of the FATSI test to enrich for patients exhibiting these alterations at the genomic level.

Supported by an NCI R01 and The NCI Cancer Therapy and Evaluation Center Phase II contract we screened >600 patients in a clinical trial for foci formation deficiency [Villalona-Calero et al., 2016]. Functional deficiency was found in 29% of solid tumor patients. We also showed that it is safe to administer the PARP inhibitor veliparib at doses up to 300 mg per day to patients with FA deficient

tumors, and that veliparib can be safely combined with the DNA damaging agent mitomycin C. Activity was seen for the combination in heavily pretreated patients [Villalona-Calero et al., 2016]. Veliparib as a single agent, showed clinical activity in BRCA/RAD51 germline mutated breast cancer, initially identified through FATSI. However, PARP trapping, rather than PARP inhibition, appears to be a better measure of the activity of PARP inhibitors and veliparib has been demonstrated to be a weaker PARP trapping agent compared to agents such as olaparib and niraparib [Murai et al., 2012; Murai et al., 2014].

4.1 Background

Pembrolizumab is a potent humanized immunoglobulin G4 (IgG4) monoclonal antibody (mAb) with high specificity of binding to the programmed cell death 1 (PD-1) receptor, thus inhibiting its interaction with programmed cell death ligand 1 (PD-L1) and programmed cell death ligand 2 (PD-L2). Based on preclinical in vitro data, pembrolizumab has high affinity and potent receptor blocking activity for PD-1. Pembrolizumab has an acceptable preclinical safety profile and is in clinical development as an intravenous (IV) immunotherapy for advanced malignancies. Pembrolizumab is indicated for the treatment of patients across a number of indications because of its mechanism of action to bind the PD-1 receptor on the T cell. For more details on specific indications refer to the Investigator brochure.

Investigators should be familiar with the current olaparib (AZD2281) Investigator Brochure (IB).

Olaparib (AZD2281, KU-0059436) is a potent Polyadenosine 5'diphosphoribose [poly (ADP ribose)] polymerisation (PARP) inhibitor (PARP-1, -2 and -3) that is being developed as an oral therapy, both as a monotherapy (including maintenance) and for combination with chemotherapy and other anti-cancer agents.

PARP inhibition is a novel approach to targeting tumors with deficiencies in DNA repair mechanisms. PARP enzymes are essential for repairing DNA single strand breaks (SSBs). Inhibiting PARPs leads to the persistence of SSBs, which are then converted to the more serious DNA double strand breaks (DSBs) during the process of DNA replication. During the process of cell division, DSBs can be efficiently repaired in normal cells by homologous recombination repair (HR). Tumors with HR deficiencies (HRD), such as ovarian cancers in patients with BRCA1/2 mutations, cannot accurately repair the DNA damage, which may become lethal to cells as it accumulates. In such tumor types, olaparib may offer a potentially efficacious and less toxic cancer treatment compared with currently available chemotherapy regimens.

BRCA1 and BRCA2 defective tumors are intrinsically sensitive to PARP inhibitors, both in tumor models *in vivo* [Rottenberg et al., 2008; Hay et al., 2009] and in the clinic [Fong et al., 2009]. The mechanism of action for olaparib results from the trapping of inactive PARP onto the single-strand breaks preventing their repair [Helleday, 2011; Murai et al 2012]. Persistence of SSBs during DNA replication results in their conversion into the more serious DNA DSBs that would normally be repaired by HR repair. Olaparib has been shown to inhibit selected tumor cell lines *in vitro* and in xenograft and primary explant models as well as in genetic BRCA knock-out models, either as a stand-alone treatment or in combination with established chemotherapies.

A detailed description of the chemistry, pharmacology, efficacy, and safety of olaparib is provided in the Investigator's Brochure.

